9.2.3 Overall Survival (OS) and Progression-Free Survival (PFS)

PFS is defined as the duration of time from start of treatment to time of progression or death. Patients who have not yet progressed or died will be censored at the time of their last follow-up.

All patients will be followed for a minimum of 2 years, so that their actual 2-year OS and PFS can be determined. OS is defined as the time from start of treatment to time of death. Patients who have not yet died will be censored at the time of their last follow-up.

Tumor recurrence will be assessed minimally at week A25, and patients will be followed with MRI scans and clinical visits as standard of care. Even though we cannot schedule precise time points for follow-up MRIs (because that portion is not a part of the study), we will obtain 2-year PFS as exploratory data. Since LGGs are infiltrative tumors which typically do not enhance with contrast administration, for evaluation of response and PFS,

12 April 2020 Page 64 of 88 confidential

the tumor (i.e., target lesion) will be measured from the T2 or FLAIR MRI images. In case there is an enhancing lesion at the baseline, careful discussion will be made as to whether the pathology information as WHO grade II tumor truly represents the status of the tumor. If the enhancing tumor is still considered to be grade II, the size of the enhancing lesion will be used for evaluation.

9.2.4 Evaluation of PBMC responses against IMA950 in association with OS, PFS and frequency of IMA950 reactive T-cells in the tumor

We will attempt to determine whether vaccine-reactive T-cells in PBMC: 1) correlate with clinical benefits, such as PFS and OS; 2) correlate with observations in the glioma TME; and 3) is higher in Arm 1 over Arm 2 patients.

9.2.5 To tabulate tumor objective response rate (ORR) (According to LGG RANO if there is measurable tumor after surgery).

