5.5.8 Study Procedures Post-Vaccine Follow-up

All patients, including those who discontinue protocol therapy early, will be followed for response and toxicity assessments until disease progression, start of a new therapy, or for a maximum of 24 months from study registration (whichever occurs earlier). Follow-up visits should be scheduled per standard-of-care for patients with stable WHO grade II glioma without active treatment (every 3 months). As overall survival is an endpoint of the study, subjects who discontinue protocol therapy must continue to be followed (every 3 months) for survival until death or the conclusion of the study.

For any patient with regimen limiting toxicity (RLT), follow-up will continue as medically appropriate for the specific toxicity until resolution to grade 1 or better or 3 months of no change (stabilization).

If treatment is discontinued for progression, the final study visit will be the final off-study visit, providing there is no ongoing grade 2 or greater treatment related toxicity.

- Physical/neurological examination
- Vital signs
- Interval medical history
- KPS
- Review of concurrent medications
- Adverse event assessment
- MRI scan
- Complete blood count (CBC) with differential and platelet count
- Blood chemistry assessment, including:
 - Alkaline phosphatase, aspartate aminotransferase/alanine aminotransferase (ALT/AST), total bilirubin, calcium, blood urea nitrogen (BUN), creatinine, total protein, albumin, random glucose, potassium, sodium, chloride, bicarbonate.

Serum chemistry and CBC tests are required at the first follow-up visit or when previous tests demonstrated any abnormality. If a patient does not show any abnormality during the course or at the first follow-up visit, that patient will not require CBC and chemistry on the follow-up visits per protocol.

12 April 2020 Page 37 of 88 confidential

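### For patients still progression-free, the 24-month cap from registration ends response follow-up short of the 2 years from start of treatment that Section 9.2.3 promises

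*Combined protocol and SAP*

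**What the plan says.** Section 9.2.3 sets the PFS clock: "PFS is defined as the duration of time from start of treatment to time of progression or death". It then commits to a follow-up length: "All patients will be followed for a minimum of 2 years, so that their actual 2-year OS and PFS can be determined". Its censoring rule is: "Patients who have not yet progressed or died will be censored at the time of their last follow-up". It notes that follow-up MRIs are standard of care and cannot be scheduled precisely, but still says "we will obtain 2-year PFS as exploratory data".

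Section 5.5.8 follows all patients for response and toxicity "until disease progression, start of a new therapy, or for a maximum of 24 months from study registration (whichever occurs earlier"). Footnote 4 of the calendar in Section 6 repeats this limit. On visit timing, Section 5.5.8 says: "Follow-up visits should be scheduled per standard-of-care for patients with stable WHO grade II glioma without active treatment (every 3 months").

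Survival is handled separately in Section 5.5.8: "subjects who discontinue protocol therapy must continue to be followed (every 3 months) for survival until death or the conclusion of the study".

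Section 12.1.5 plans Kaplan-Meier estimates of OS and PFS with Greenwood confidence regions. It names no 2-year landmark and gives no rule for reading the curve beyond the last time at risk.

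**The concern.** One section gives a minimum of two years counted from treatment. Another gives a maximum of 24 months counted from registration, which comes first: Section 4.2 provides for patients who are registered and then cannot begin treatment. For a patient without an event, both can hold only if registration and first treatment fall on the same day.

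The patients affected are those who are progression-free late in follow-up, and a 2-year PFS estimate depends on them being under observation at month 24. If the last of them is censored earlier, the Kaplan-Meier curve ends before month 24. The promised figure is then either not estimable or gets replaced by an earlier, higher point on the curve. Section 12.1.6 also relates immune response to PFS, so it uses the same follow-up data.

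**Working it through.** **Inputs from the documents**
- PFS origin: start of treatment (9.2.3). Cap: 24 months from registration (5.5.8; calendar footnote 4).
- Randomization: within 2 weeks of enrollment (calendar footnote).
- Surgery: at most 35 days from randomization, stated for a craniotomy delayed for non-toxicity reasons (5.7.1). First vaccine: day -23±2.
- Week A1: no later than 10 weeks after surgery and at least 2 weeks after the post-operative steroid taper (5.5.4). Week A25 is 24 weeks after A1.
- Follow-up visits: every 3 months (5.5.8).
- Median PFS in the earlier low-grade glioma vaccine studies: 17 and 12 months from first vaccine (2.7).

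**Assumptions**
- Enrollment and registration are the same date, and the 35-day limit also bounds surgery that is not delayed.
- A1 falls 2 to 10 weeks after surgery, and the 3-monthly visits are counted from A25.
- PFS is exponential; the earlier medians only illustrate size.
- One month is 30.44 days.

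**Step 1. Gap from registration to first treatment.** Enrollment to randomization is 0 to 14 days. Randomization to first vaccine is at most 35 − 21 = 14 days. The total is 0 to 28 days.

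**Step 2. Longest window on the PFS clock for an event-free patient**, 24 − gap/30.44:

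| Gap (days) | Window (months) |
|---|---|
| 0 | 24.0 |
| 7 | 23.8 |
| 14 | 23.5 |
| 28 | 23.1 |

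The 2-year minimum is met only at a gap of zero.

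**Step 3. Last visit inside the cap.** A25 falls (23 + 7 × weeks to A1 + 168)/30.44 months after first treatment; 3-month steps are added until the cap.

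| A1, weeks after surgery | A25 (months) | Last visit, gap 0 | Gap 14 days | Gap 28 days |
|---|---|---|---|---|
| 2 | 6.7 | 21.7 | 21.7 | 21.7 |
| 4 | 7.2 | 22.2 | 22.2 | 22.2 |
| 6 | 7.7 | 22.7 | 22.7 | 22.7 |
| 8 | 8.1 | 23.1 | 23.1 | 20.1 |
| 10 | 8.6 | 23.6 | 20.6 | 20.6 |

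The range is 20.1 to 23.6 months. Even with no gap, the visit grid stops short of month 24.

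**Step 4. Overstatement if the last earlier value is read as 2-year PFS**, 0.5^(t/median) − 0.5^(24/median):

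| Last visit t (months) | Median 12 | Median 17 |
|---|---|---|
| 20.1 | 31.3% − 25.0% = 6.3 points | 44.1% − 37.6% = 6.5 points |
| 20.6 | 30.5% − 25.0% = 5.5 points | 43.2% − 37.6% = 5.6 points |
| 22.2 | 27.7% − 25.0% = 2.7 points | 40.5% − 37.6% = 2.9 points |
| 23.6 | 25.6% − 25.0% = 0.6 points | 38.3% − 37.6% = 0.7 points |

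**Step 5. Patients whose 2-year status is known anyway.** With a 28-day gap, the share with an event inside the window is 1 − 0.5^(23.1/median): 74% for a median of 12 months and 61% for 17 months, or about 22 and 18 of 30 patients (15 per arm, Section 12.1.2). Events falling between the cap and month 24 are about 1% of patients.

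**The case against.** A reader might infer that 2-year PFS cannot be observed in any patient. The documents do not support that. A patient who progresses or dies before the cap has a known status, and Step 5 suggests this could be most patients. Nor is 2-year OS blocked, because the survival follow-up in Section 5.5.8 does not carry the 24-month limit.

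A reader might also settle on a bias of about 5 points. That needs particular combinations of a late A1, a gap of about two weeks or more, and a rigid visit grid. With A1 at 4 to 6 weeks the figure is about 2 to 3 points at any gap from 0 to 28 days. A1 dates will differ between patients, so the pooled curve runs to the latest last visit and not to the earliest. The grid is itself an assumption: footnote 4 gives 3 months only as an example, and Section 9.2.3 says scan times cannot be fixed. The cap alone removes 0 to about 4 weeks; most of the shortfall comes from the grid. The plan contains no carry-forward rule, and the value at 24 months could properly be reported as not estimable.

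Precision matters too. Around 38%, an approximate 95% interval is ±1.96 × √(0.38 × 0.62/30), about ±17 points, or about ±25 with 15 per arm. Section 9.2 says these endpoints are not sufficiently powered and will be tabulated.

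All of this stands and limits the consequence. It does not remove the contradiction. The standard-of-care sentence in Section 9.2.3 explains irregular scan timing; it does not lift the stop in Section 5.5.8.

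**Conclusion.** The plan is wrong as written, with limited consequence. Followed literally, Section 5.5.8 and footnote 4 cannot deliver the 2-year minimum of Section 9.2.3 for a patient who stays progression-free, unless treatment starts on the day of registration. The stated actual 2-year PFS is therefore not assured.

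Under the assumptions listed, the last assessment falls at 20.1 to 23.6 months, and substituting the last earlier value would overstate 2-year PFS by 0.6 to 6.5 points, depending on schedule. If registration takes place at consent, as Section 4.1 may imply, the gap could exceed 28 days: 56 days would leave a window of 22.2 months.

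The point concerns exploratory PFS in event-free patients only. No sample size, stopping rule or primary conclusion depends on it.

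**What to change.** In Section 5.5.8 and calendar footnote 4, run the response follow-up cap from first study treatment. Add a closing progression assessment at or after 24 months within a stated window, for example up to 3 months, using the standard-of-care scan, and let the cap extend to that assessment. Both parts are needed: moving the origin alone gives a 24.0-month window, but the last 3-monthly visit could still fall before month 24. Sections 5.5.8 and 9.2.3 and footnote 4 would then agree. Follow-up would still end earlier for patients who start a new therapy, so Section 9.2.3 should say how PFS treats them.

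If the sponsor prefers to keep the present cap, Section 9.2.3 should drop the claim of an actual 2-year PFS, and Kaplan-Meier PFS should be reported only to the last time at which patients are at risk.

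The cost is protocol wording and the recording of one later standard-of-care visit for event-free patients. Treatment and sample size are unchanged.

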We recently completed a bi-institutional pilot study of s.c. vaccinations with synthetic peptides for GAA epitopes and the tetanus toxoid peptide emulsified in Montanide-ISA-51 every 3 weeks for 8 courses, and i.m. administration of poly-ICLC in human leukocyte antigen (HLA)-A2⁺ patients with: newly diagnosed high-risk LGG without prior RT (UPCI 07-057: Cohort 1); newly diagnosed high-risk LGG with prior RT (UPCI 07-057: Cohort 2); and recurrent LGG (UPCI 08-135). Primary endpoints were safety and CD8⁺ T-cell responses against vaccine-targeted GAAs, assessed by Enzyme-Linked Immuno-SPOT (ELISPOT) assays. Treatment response was evaluated clinically and by MR imaging. Targeted GAAs were EphA2, IL-13Rα2, survivin, and WT1.

In the UPCI 07-057 study, high-risk subsets of these LGG patients are defined as astrocytoma or oligoastrocytoma histology plus any one of the following conditions: 1) age ≥40 with any extent resection; 2) age 18-39 with incomplete resection; or 3) age 18-39 with neurosurgeon-defined gross total resection with tumor size ≥ 4 cm in diameter. We enrolled 13, 1 and 10 patients in UPCI 07-057 Cohorts 1, 2 and UPCI 08-135, respectively. No dose-limiting non-CNS toxicities have been encountered except for one case with Grade 3 fever (UPCI 07-057: Cohort 1). ELISPOT assays demonstrated robust IFN-γ responses against at least 3 of the 4 GAA epitopes in 10 and 4 cases of Cohorts 1 and 3, respectively. Cohort 1 patients demonstrated significantly higher IFN-γ responses than Cohort 3 patients.

Median progression-free survival (PFS) periods since the 1st vaccine was 17 months in Cohort 1 (range 10-47+) and 12 months in Cohort 3 (range 3-41+). Only one patient with a large astrocytoma in Cohort 2 has been progression-free for over 67 months. Although further follow-up is required to mature PFS data, our results demonstrate that the regimen in these patients is well tolerated, and induces robust type-1 anti-GAA T-cell responses. These data also suggest that patients with LGG are suitable for vaccine therapy.

12 April 2020 Page 22 of 88 confidential

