3.1 Inclusion Criteria

- **3.1.1** Patients must be ≥ 18 years old
- 3.1.2 Pathological criteria Patients must have a newly diagnosed or recurrent WHO grade II astrocytoma, oligoastrocytoma or oligodendriglioma that has been histologically confirmed by prior biopsy or surgical resection. If the pathological diagnosis was made outside of UCSF, the pathology must be reviewed and confirmed at UCSF.
- **3.1.3** Patients must be positive for HLA-A2 based on flow-cytometry or genotyping.
- **3.1.4** Before enrollment, patients must show non-enhancing T2-FLAIR lesions that are amenable to surgical resection. Surgical resection of at least 0.3 grams of tumor is expected to ensure adequate evaluation of the study endpoints.
- 3.1.5 Prior radiation therapy (RT) after initial diagnosis will be allowed but there must be at least 6 months from the completion of RT (or radiosurgery). Prior chemotherapy and any systemic molecularly targeted anti-tumor therapy will be allowed, and there must be at least 28 days from the last temodar chemotherapy, 42 days for nitrosourea; at least 14 days from the last dose for chemotherapy regimens given continuously or on a weekly basis with limited potential for delayed toxicity.

12 April 2020 Page 24 of 88 confidential

- **3.1.6** Karnofsky performance status (KPS) ≥ 70% (Appendix I)
- **3.1.7** Off or low dose (≤ 4 mg/day by Decadron) corticosteroid for at least for 2 weeks before the first pre-surgical vaccine
- 3.1.8 Adequate organ function within 28 days of study registration including:
 Adequate bone marrow reserve: absolute neutrophil (segmented and bands) count (ANC) ≥1.0 x 10⁹/L, absolute lymphocyte count (ANC) ≥4.0 x 10⁸/L, platelets ≥100 x 10⁹/L; hemoglobin ≥ 8 g/dL
 - Hepatic: Total bilirubin \leq 1.5 x upper limit of normal (ULN) for age and SGPT (ALT) \leq 2.5 x upper limit of normal (ULN) for age
 - Renal: Normal serum creatinine or creatinine clearance ≥60 ml/min/1.73 m²
- **3.1.9** Must be free of systemic infection. Subjects with active infections (whether or not they require antibiotic therapy) may be eligible after complete resolution of the infection. Subjects on antibiotic therapy must be off antibiotics for at least 7 days before beginning treatment.

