If both arms are found tolerable, then subsequent patients will then be randomized into one of the two arms for the pre-surgical part of the study. **Arm 1**: Patients will receive IMA950-poly-ICLC vaccine plus varlilumab. **Arm 2**: Patients will receive IMA950-poly-ICLC vaccine alone. The randomization will take place in a 1:1 ratio between the two arms with the stratification based on whether the patient is newly diagnosed vs. recurrent.

Patients will be assigned to treatment by means of the UCSF Biostatistics Facility randomization system in an open label fashion. Information on the two arms will be loaded into the database and the treatment arm assigned to the subjects when the subject's initials and ID# are entered into the program. Results of randomization will not be blinded, and no placebo will be used.

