9.2 Exploratory Objectives

As this study is not sufficiently powered to evaluate the following endpoints, data will be tabulated.

9.2.1Evaluation of IMA950-reactive T-cell infiltration and CXCL9/10 expression in tumors resected from Arm 1 and Arm 2 patients

12 April 2020 Page 63 of 88 confidential

In surgically resected tumor tissues from Arm 1 (IMA950+poly-ICLC and varlilumab) and Arm 2 (IMA950+poly-ICLC alone) patients, we will evaluate numbers of tumor-infiltrating CD4+ T-cells CD8+ T-cells (by flow-cytometry) and CXCL10 expression (by RT-PCR). Among T-cells, we will evaluate IMA950-reactive populations by flow-cytometry. We will perform preliminary comparisons of these readouts between Arm 1 and Arm 2 patients. In our separate vaccine study using GBM6-PD lysate (IRB# 15-17078 vaccine study), there will be samples from the control group who received no therapy prior to surgery. Hence these samples will be also used to assess whether IMA950+poly-ICLC vaccine in the current study (and varlilumab in Arm 1) increases the number of T-cells in the tumor site.

9.2.2 To evaluate IMA950-reactive T-cell receptor (TCR) clonotypes in tumors resected from Arm 1 and Arm 2 patients

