- **12.1.5 Exploratory Efficacy Objective:** To estimate overall survival (OS) and progression-free survival (PFS) in the two arms. Product limit (Kaplan-Meier) estimates of the OS and PFS functions will be calculated with 95% Greenwood confidence regions. The trial is not adequately powered for the log-rank test that compares survival functions between arms.
- **12.1.6 Exploratory Efficacy Objective:** Evaluation of PBMC responses against IMA950 in association with OS, PFS and frequency of IMA950 reactive T-cells in the tumor. The association of the immunological parameter with PFS and OS will be evaluated using proportional hazards (Cox) regression. Frequencies will be tabulated.
- **12.1.7 Exploratory Efficacy Objective:** Tabulate tumor objective response rate (ORR). The (multinomial) distributions of responses in patients with measurable tumors (Section 9.2.3) will be calculated with simultaneous (Sison & Glaz) confidence regions. The trial is not adequately powered for a comparison between arms using Fisher's exact test.
- **12.1.8 Exploratory Efficacy Objective:** Evaluation of leukocyte phenotypes in PBMC samples. Frequencies will be tabulated to compare the distributions of the phenotypes between arms.
- **12.1.9 Exploratory Efficacy Objective**: Evaluation of pharmacokinetics for varlilumab. The purpose of this exploratory efficacy objective is to capture minimum and maximum values for the different pharmacokinetics measures. The purpose is not testing hypothesis; therefore descriptive statistics will be reported.

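### The Cox analysis of blood immune response against PFS and OS omits newly diagnosed v recurrent status, so a response with no effect would tend to look slightly protective for PFS.

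*Combined protocol and SAP*

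**What the plan says.** Objective 1.2.4 asks whether blood responses to IMA950 are associated with PFS; section 9.2.4 adds OS: "We will attempt to determine whether vaccine-reactive T-cells in PBMC: 1) correlate with clinical benefits, such as PFS and OS". The method is in section 12.1.6: "The association of the immunological parameter with PFS and OS will be evaluated using proportional hazards (Cox) regression". Neither place names a stratum or a covariate.

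The population is mixed. Section 3.1.2 states: "Patients must have a newly diagnosed or recurrent WHO grade II astrocytoma" (the list of histologies continues). Section 4.1 randomises 1:1 "with the stratification based on whether the patient is newly diagnosed vs. recurrent". No analysis in section 12 uses that factor.

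Section 2.7 describes the earlier UPCI studies: "We enrolled 13, 1 and 10 patients in UPCI 07-057 Cohorts 1, 2 and UPCI 08-135, respectively". It reports robust responses in 10 cases of Cohort 1 and 4 of Cohort 3, and adds: "Cohort 1 patients demonstrated significantly higher IFN-γ responses than Cohort 3 patients". On outcome it says: "Median progression-free survival (PFS) periods since the 1st vaccine was 17 months in Cohort 1 (range 10-47+) and 12 months in Cohort 3", and notes that the PFS data still need further follow-up. Cohort 3 is not defined there; I read it as the recurrent study, UPCI 08-135.

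Section 9.2 limits the exploratory endpoints: "As this study is not sufficiently powered to evaluate the following endpoints, data will be tabulated".

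**The concern.** The arms are randomised; responders and non-responders are not. Stratifying the randomisation balances disease status between arms but not between patients who respond and patients who do not. If newly diagnosed patients both respond more often and progress later, responders will contain more of them. A Cox model without disease status then credits the response with part of the better prognosis. The error runs in the direction the investigators hope to see, and a larger sample would not remove it. At stake is whether an association reported under objective 1.2.4, and carried into later vaccine trials, reflects the response or the case mix.

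**Working it through.** **1. The plan's own figure.** No figure is given for this association. The only immunological power statement is in 12.1.2: 15 per arm, difference 0.8, SD 1.0, one-sided 0.10, power 80%. The noncentrality is 0.8/√(2/15) = 2.19. The normal approximation gives Φ(2.19 − 1.28) = 81.8%, and the exact t calculation gives 81.0%. The figure reproduces, and it supplies n = 30.

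**2. Inputs.**
- From section 2.7: response rates 10/13 = 0.769 (newly diagnosed) and 4/10 = 0.400 (recurrent), with numbers enrolled as denominators; median PFS 17 and 12 months.
- From section 5.5.8: progression follow-up of at most 24 months, used as the censoring time.
- Assumed: half the patients newly diagnosed (30% to 70% as a range), exponential PFS, a binary responder known at time zero, and no effect of response within either disease group.

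**3. Case mix by response, equal split.**
- Responders: 0.769/(0.769 + 0.400) = 66% newly diagnosed.
- Non-responders: 0.231/(0.231 + 0.600) = 28% newly diagnosed.

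**4. Spurious hazard ratio.** Set the newly diagnosed hazard to 1; the recurrent hazard is then 17/12 = 1.417.
- Responders: 1 + 0.342 × 0.417 = 1.143.
- Non-responders: 1 + 0.722 × 0.417 = 1.301.
- Ratio: 1.143/1.301 = 0.88, a log hazard ratio of −0.13.

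**5. Size against sampling error.**
- Expected events: 15 × (1 − 2^(−24/17)) + 15 × (1 − 2^(−24/12)) = 15 × 0.624 + 15 × 0.750 = 20.6, about 21.
- Responder share: (0.769 + 0.400)/2 = 0.585. Approximate SE: 1/√(21 × 0.585 × 0.415) = 0.44.
- Shift: 0.13/0.44 = 0.29 standard errors.
- Falsely protective at one-sided 0.10: Φ(−1.28 + 0.29) = 16%. At one-sided 0.025: Φ(−1.96 + 0.29) = 5%.
- Chance that the estimate falls below 1: Φ(0.29) = 61%, against 50% without bias.

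**6. Simulation of the Cox model.**

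| Quantity | Unadjusted | Stratified by disease status |
|---|---|---|
| Large-sample HR, 30% to 70% newly diagnosed | 0.87 to 0.90 | 1.00 to 1.01 |
| Falsely protective, one-sided 0.10, n = 30 | 16% to 19% | 10% to 12% |
| Falsely protective, one-sided 0.025, n = 30 | about 5% (up to 5.5%) | 2% to 3% |

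For a continuous response shifted by 1 SD between disease groups (assumed), the spurious hazard ratio is 0.93 to 0.94 per SD. The falsely protective rate at one-sided 0.025 is again about 5%.

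**7. How firm the earlier contrast is.** The PFS hazard ratio from the medians is 12/17 = 0.71. Even if all 23 patients had events, the SE is √(1/13 + 1/10) = 0.42, giving a 95% CI of 0.31 to 1.61 (p about 0.41). For 10/13 v 4/10, Fisher's exact p is 0.10; section 2.7 calls the IFN-γ levels, not these counts, significantly different.

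**The case against.** The plan calls these endpoints underpowered and exploratory, and speaks of association, not causation. The bias of 0.13 on the log scale is about a quarter of the standard error. The earlier evidence is 23 patients treated with other antigens (EphA2, IL-13Rα2, survivin, WT1), Montanide and intramuscular poly-ICLC, and measured by ELISPOT. Its Cohort 1 was limited to high-risk patients without prior radiotherapy. Section 8.1 makes tetramer magnitude the primary measure and responder status exploratory, whereas the main calculation uses a binary responder. Section 12.1.6 sets no significance level, so 0.10 is borrowed from 12.1.2. At the plan's own figures stratifying also has the larger root-mean-square error: with simulated SEs of 0.46 unadjusted and 0.51 stratified, √(0.46² + 0.13²) = 0.48 against 0.51.

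Most of this stands and limits how strongly the point can be put. It does not remove the point. Low power describes imprecision, while confounding shifts the estimate at any sample size. Section 12.1.6 goes beyond tabulation by committing to a Cox regression. The continuous predictor gives a similar falsely protective rate. The factor is already recorded and was judged important enough to stratify the randomisation.

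**Conclusion.** The point holds as a modest bias that is cheap to correct. Disease status is associated with both response and PFS in the plan's own background, yet it is absent from the model relating the two. On those figures a response with no effect would tend to look slightly protective, with falsely protective findings at roughly 1.6 to 2 times the nominal rate. This rests on the assumed mix, exponential PFS, the reading of Cohort 3, and transfer of the earlier response and PFS contrasts to this vaccine and assay.

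A reader might infer more, and the documents do not support it:
- **That disease status drives both response and PFS.** The PFS contrast is untested and immature, with overlapping ranges.
- **That OS is biased in the same way.** No OS by cohort is reported, so this is conjecture.
- **That a null response would reliably look protective.** The estimate falls below 1 about 61% of the time, not nearly always.
- **That the bias is large.** Recurrent medians of 8 or 6 months would give hazard ratios of about 0.76 to 0.79 or 0.69 to 0.73, but neither median comes from the documents.
- **That the blood-tumour association is confounded too.** Nothing in the documents shows this, and 12.1.6 only tabulates those frequencies.

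**What to change.** In 12.1.6, with a matching line in 9.2.4, state that the Cox models for PFS and OS are stratified by newly diagnosed v recurrent status (or adjusted for it). Report that hazard ratio as the main association, show the unadjusted one beside it, and label both hypothesis-generating.

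This takes about one sentence and no new data. The price is precision: with about 21 events, stratifying raises the standard error of the log hazard ratio by roughly 10% to 20% (0.46 to 0.51 in one simulation, a rise of 11%). Showing both estimates lets readers see that trade.
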